#### **4.1.5.3 Risks of insertional mutagenesis and oncogenesis**

The possibility of oncogenic events due to vector-mediated insertional mutagenesis cannot be excluded with certainty, but available evidence suggests it to be unlikely given that (i) AAV vector genomes integrate into host chromosomes at a very low frequency (Nowrouzi, *et al* 2012), (ii) a limited number of AAV particles will be administered, and (iii) the eye predominantly contains non-dividing cells and consequently ocular tumours are very rare. Furthermore, oncogenesis has not been reported following injection of AAV into thousands of rodent eyes. Even when we injected AAV vectors intraocularly in a large number of tumour-prone *p53*-/- mice, we found no evidence of malignant transformation of retinal cells (Balaggan, *et al* 2012). In the highly unlikely event that an intraocular tumour does arise, the comprehensive monitoring procedures described in Section 5.4.2.3 of the protocol will enable early detection and thus prompt appropriate management.

#### **4.1.5.5 Risk of surgical adverse effects**

The risk of significant surgical adverse effects is similar to the standard surgical care for other common forms of vitreo-retinal disorders, including bleeding in the eye, infection and increased pressure inside the eye. To manage the risk of surgical adverse events, only highly experienced surgeons will perform

### **Gene Therapy for Achromatopsia (CNGA3)**

---

the procedure. Complications of surgery are typically managed effectively by medication or further surgical intervention but can rarely result in lasting harm to sight. The risk of lasting severe impairment of sight from vitrectomy surgery is approximately 1 in 1000. Reduction in foveal retinal thickness has been previously reported in a proportion of patients in both our first RPE65 trial and other RPE65 clinical trials, believed to result from temporary retinal detachment which is a deliberate consequence of targeted administration of the vector suspension, but no other significant surgical adverse effects. However, in subsequent trials the use of a modified surgical technique that minimises the height of retinal detachment has resulted in no significant effect on foveal retinal thickness – most notably retinal thickness has been stable post-intervention in all 23 participants (11 adults and 12 children) in the CNGB3 trial.

Delivery of ATIMP to the subretinal space will be performed by standard surgical vitrectomy. This will involve a 3-port pars plana vitrectomy followed by injection of ATIMP using a fine cannula through small retinotomies, resulting in a temporary retinal detachment. Previous gene therapy clinical trials have shown that the bleb of subretinal ATIMP suspension can be expected to resolve spontaneously over the course of the first 24 to 48 hours postoperatively as the fluid is absorbed by the underlying retinal pigment epithelium.

Potential complications of this surgery specifically include persistence of the subretinal vector bleb, the development of retinal tears, elevated intraocular pressure and persistent postoperative intraocular inflammation. Persistently elevated intraocular pressure may result in glaucoma and vision loss; likewise, persistent inflammation may result in vision loss. Elevated intraocular pressure will be managed by topical therapy; with systemic therapy where indicated with specialist advice sought as required. Any potential risk to visual function will be minimised by limiting ATIMP delivery to the area of retina most likely to benefit, and by leaving the contralateral eye untreated. Retinal detachment caused by persistent vector bleb or intraoperative retinal tear is expected to occur in fewer than 1 in 100 procedures and can be effectively managed in the majority by retinopexy, with or without intraocular tamponade. Vitrectomy surgery is a standard technique, commonly performed for a wide range of indications. Injection of fluids under the retina is less commonly performed but is a standard step in surgery for subretinal haemorrhage, and an adjunctive technique in the management of retinal detachment.

#### ***4.1.5.6 Risk of adverse effects of corticosteroids***

Candidates will be screened for contra-indications to transient immune suppression by corticosteroids; in particular, a history of uncontrolled hypertension, diabetes mellitus, tuberculosis, renal impairment, osteoporosis, gastric ulceration, severe affective disorder immunocompromised status and increased risk of infections. Possible adverse effects of short-term systemic corticosteroid use include increases in blood pressure and blood sugar, weight gain, changes in mood or behaviour, increased risk of infections, increased intraocular pressure and cataracts. Local steroids used on or near the eye can cause increased intraocular pressure and cataracts. The possibility of steroid-induced adverse effects will be monitored regularly. In particular, blood pressure and blood glucose will be measured, as will renal function and liver function (at baseline, 1 day, 7 days, 2 weeks and 4 weeks after surgery). Common and expected laboratory findings observed in the other ongoing studies utilising prophylactic corticosteroids have included but are not limited to: leucocytosis, neutrophilia, hyperglycaemia. If the latter should occur, then a referral to a diabetologist would occur. On occasion

## Gene Therapy for Achromatopsia (*CNGA3*)

---

mild transaminase changes have occurred but are mild and self-limiting. All the above have resolved with the tapering of the corticosteroids.

### *4.1.5.7 Risks of investigations performed during assessment and follow up*

The majority of investigations are non-invasive routine clinical tests and presents no significant risk. Venepuncture causes temporary discomfort, occasionally bruising/swelling and rarely infection at the site of puncture. The participants will have all risks discussed during the consent process and are able to read them additionally in the Participant Information Sheet (PIS).

### *4.1.5.8 Risk of rod photoreceptor dysfunction*

The aim of the intervention is to improve the function of cone photoreceptor cells. Rod photoreceptors exposed to the ATIMP are not expected to benefit but may be subject to adverse effects of the surgical intervention or ATIMP. We plan to minimize any adverse effect by targeting the ATIMP to the central retina where the cone photoreceptors predominate. In addition, the use of a cone specific promoter to drive *CNGA3* expression specifically in cones, will minimise inappropriate ectopic expression in rod photoreceptors. Moreover, should cone photoreceptor-mediated vision be improved by the gene therapy, any dysfunction of rod photoreceptor cells is expected to be evident only in a dimly illuminated environment.

No change in rod function has been described to date in the animal models (mouse and dog) used to demonstrate the potential of gene supplementation therapy in *CNGA3*-associated Achromatopsia.

There has also been no change in rod function in any of the 23 participants (11 adults and 9 children) in our current CNGB3 trial.

### *4.1.5.9 Risk of thinning of the fovea*

Thinning of the retina in the macula (macular thinning) has been detected in 6/10 participants after subfoveal delivery of AAV vector in our previous RPE65 clinical trial (MGT003). Macular thinning was typically apparent within 3 months and subsequently non-progressive. Associated thinning of the photoreceptor cell (outer nuclear) layer was evident, with variable disruption of the photoreceptor ellipsoid (inner segment) zone. However, in subsequent current trials the use of a modified surgical technique that minimises the height of retinal detachment has resulted in no significant effect on retinal thickness – most notably retinal thickness has been stable post-intervention in all 23 participants (11 adults and 9 children) in the CNGB3 trial.

Since the central macula comprises predominantly of cone photoreceptor cells that have no function in achromatopsia, therefore it is not expected that macular thinning to affect vision significantly in this trial. The participants intensive schedule of assessments (Table 5.6) has been designed to assess vision frequently.

### *4.1.5.10 Risk of visual imbalance*

Individuals affected by Achromatopsia have severe sight impairment with no colour perception from birth. Improvement of retinal function by intervention later in development is expected to lead to new visual experiences. While these are expected to be positive, unpleasant visual sensations might also be experienced. The participants are made aware of this risk from the initial consenting process.

## Gene Therapy for Achromatopsia (*CNGA3*)

---

### 4.1.5.11 Conclusion on the risk-benefit ratio

In summary, the risks associated with the intervention are justified by the potential for individual participants to benefit, and by the scientific value of the trial to the development of treatments for other individuals similarly affected. Emerging safety data from the ongoing *CNGB3* Achromatopsia trial provides further justification for the administration of vector to children in the dose escalation part of the current trial.

### 4.1.6 Explanation for Choice of Comparators

There is no currently approved treatment for Achromatopsia caused by mutations in *CNGA3*. The comparator will be the contralateral eye and supplementary data collected as part of a prospective, parallel natural history study of patients with Achromatopsia.

The totality of the data from paediatric subjects enrolled in the UK and adult subjects enrolled in the U.S. will be reviewed and inform the design of a future Phase II interventional study.

## 4.2 Objectives

### 4.2.1 Primary Objective

The primary research objective is to assess the safety of an AAV2/8 vector for *hCNGA3* gene replacement in the retina. Safety is defined as:

Safety is defined as the absence of an ATIMP-related:

- Reduction in visual acuity by 15 ETDRS letters or more that fails to resolve to within 15 letters of baseline in a 4-week period once prophylactic treatment commences
- Severe unresponsive inflammation (defined below)
- Infective endophthalmitis
- Ocular malignancy
- Grade III or above non-ocular SUSAR (see section 5.11.3)

Severe unresponsive inflammation will be defined according to the Standardisation of Uveitis Nomenclature (SUN) Working Group grading system (Jabs *et Al.* 2005) i.e.

- anterior chamber cells 3+ (26-50 cells in a field size of 1mm x 1-mm slit-beam), or
- anterior chamber flare 3+ (marked, iris and lens details hazy), or
- vitreous haze 3+ (Ophthalmology 1985; 92:467-71)

that fails to improve by 2 steps (or to grade 0) during a 6-week period.

### 4.2.2 Secondary Objective

The secondary research objective is to determine whether an AAV2/8 vector for *hCNGA3* gene replacement in the retina can improve retinal function, visual function and quality of life.

## 4.3 Trial Design

This is an open-label phase I/II dose-escalation trial to determine the safety and efficacy of subretinal administration of the ATIMP in children with *CNGA3*-related Achromatopsia. Paediatric participants for the purposes of this protocol are participants aged up to and inclusive of 15 years of age. As part of the risk mitigation strategy for this protocol, ATIMP administration will first be administered to at least one older child participant (11- 15 years of age) from each cohort before proceeding to younger participants.

## **Gene Therapy for Achromatopsia (CNGA3)**

---

In this dose escalation study, up to 18 participants will be administered one of 3 different doses of the ATIMP in cohorts of 3 participants at a time in the first instance. Based on emerging safety data, the SDMC will make a recommendation on the dose to administer to the next cohort of participants. The SDMC may recommend additional participants at a given dose before making their recommendation on how to proceed to the next dose.

Paediatric cases for the purposes of this protocol are defined as participants aged up to and inclusive of 15 years.

In addition to the paediatric cohorts in the UK, an additional cohort of 2 adult subjects will be enrolled in the US. The adult cohort will be administered the highest dose studied from the paediatric cohorts based on when the first adult subject is identified and ready to be enrolled. The SDMC will review the data from all subjects (paediatric and adult) in this dose escalation study.

Safety and efficacy will be assessed for 6 months following the intervention by clinical examination and special investigations according to the schedule in section 5.6 of the protocol. The totality of the data from paediatric subjects enrolled in the UK and adult subjects enrolled in the US will be reviewed and inform the design of a future Phase II interventional study.

### ***4.3.1.1 Separate longer term follow up study***

In line with current CHMP and FDA guidance, the ATIMP safety is further assessed by a separate longer term follow up study of 60 months duration, if the participants / caregiver's consent and only once they have reached the 6-month timepoint in the current study. The duration of long-term follow-up is therefore consistent with the recommendations of the current CHMP Guideline on Follow-up of Patients Administered with Gene Therapy Medicinal Products (EMA/CHMP/GTWP/60436/2007) of 22 October 2009, where it is stated that, for viral vectors without integration, latency or reactivation potential, a brief clinical history and sample testing should be performed pre-treatment, at 3, 6 and 12 months after treatment, and then yearly thereafter for a minimum of 5 years (and, if non-clinical tests or evidence from other clinical trials using identical vectors or modifications of vectors indicate a potential for integration or late re-activation, the monitoring should be extended to continue yearly after those 5 years until data indicate that there is no longer any risk to be followed). Further, although the FDA Guidance February 2020 (Long Term Follow-up After Administration of Human Gene Therapy Products: Guidance for Industry) recommends a standard 15-year period of follow-up, it is also noted that a shorter period of follow up may be appropriate if the ATIMP does not integrate and has no potential for latency and reactivation.

The follow-up study will be a non-intervention study designed to collect data on longer term safety and efficacy at the equivalent of 9, 12, 24, 36, 48 and 60 months following ATIMP administration; as such, participants in both studies will be followed up more frequently than recommended in the guidance, as additional assessments following ATIMP administration are included in the initial study (at weeks 1, 2, 4 and 6) and in the long-term follow up study (at months 9 and 18). The follow up study will have a separate protocol, participant information and consent process, and will be submitted for separate ethical review. Participants in the current study will be strongly encouraged to join the follow up study as part of their ongoing clinical review, but there will be no obligation on their part to do so. It is acknowledged that, despite encouragement, participants may elect not to participate in the long-term follow-up study; however, in this motivated population, where individuals are typically monitored by their specialist closely and regularly, this is considered unlikely.

## Gene Therapy for Achromatopsia (CNGA3)

### 4.3.2 IMP administration Review and Dose Escalation Criteria and Process

Up to 18 participants (as defined in section 4.3) will be administered a single dose of ATIMP in a total volume of 0.5mL, according to the below dose-escalation criteria. These are anticipated to be as described below:

- 1) low dose [REDACTED]
- 2) intermediate dose [REDACTED]
- 3) high dose [REDACTED]

In order to explore optimal dosing within safe limits, additional doses may be administered in order to maximise therapeutic effect, whilst maintaining the safety profile of the product. Any dose that differs from those described above will not exceed the highest titre of [REDACTED]. The Chief Investigator, Medical Monitor and SDMC chair will confirm additional doses in advance of them being administered. The actual titre to be administered will be recorded in the eCRF.

#### 4.3.2.1 Dose escalation criteria and Dose Limiting Events

Dose escalation will be managed according to review of available and emerging data on the subjects administered ATIMP top date and the occurrence, if any, of DLE's or medically important events. An SDMC will review data from a minimum of 6 weeks of follow up from each cohort of participants (at least one older child, 11-15 years of age per cohort), before recommending the next dose to be assessed in a further cohort of participants or to additional participants at the same dose level.

A DLE is defined as any of the below occurring during the 6 weeks following administration, at least possibly related to the ATIMP, not surgery alone:

- A reduction in visual acuity by 15 ETDRS letters or more that fails to resolve to within 15 letters of baseline in a 4-week period once prophylactic treatment commences
- Severe unresponsive inflammation (defined below)\*
- Infective endophthalmitis
- Ocular malignancy
- Grade III or above non-ocular SUSAR (see section 5.11.3)

\* Severe unresponsive inflammation will be defined according to the Standardisation of Uveitis Nomenclature (SUN) Working Group grading system (Jabs *et Al.* 2005) i.e.

- anterior chamber cells 3+ (26-50 cells in a field size of 1mm x 1-mm slit-beam), or
- anterior chamber flare 3+ (marked, iris and lens details hazy), or
- vitreous haze 3+ (Ophthalmology 1985; 92:467-71)

that fails to improve by 2 steps (or to grade 0) during a 6-week period.

Review of safety data will be undertaken by the SDMC prior to each dose escalation.

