#### 2. OUTCOME DEFINITIONS

### 2.1. Primary Safety Outcome

The primary safety outcome is defined as the absence/presence of any of the below events occurring during the 6 weeks following administration, at least possibly related to the ATIMP, not surgery alone:

- Reduction in visual acuity by 15 Early Treatment Diabetic Retinopathy Study (ETDRS) letters or more
- Severe unresponsive inflammation (defined in Section 4.2 of the protocol)

- Infective endophthalmitis
- Ocular malignancy
- Grade III or above non-ocular suspected unexpected serious adverse reaction (SUSAR) (Protocol MGT006, Section 5.11.3.4.2 Severity or Grading of Adverse Events).

This is the same criteria as the dose limiting event in the dose escalation phase.

Overall safety will be assessed for 6 months after the intervention in this study, and a further 4.5 years in a separate long-term follow-up study (Protocol MGT007).

The adverse events preferred terms are identified in Attachment 2.

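### The cell criterion for severe unresponsive inflammation stops at 50 cells as written, so a more inflamed eye does not meet it and could go uncounted in the primary outcome and the DLE count

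*Protocol*

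**What the plan says.** Protocol 4.2.1 (primary objective) and 4.3.2.1 (DLE definition) give the same definition of severe unresponsive inflammation. It refers to a published uveitis grading system and then, introduced by *i.e.*, lists three markers joined by *or*:

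- cells: "anterior chamber cells 3+ (26-50 cells in a field size of 1mm x 1-mm slit-beam), or"
- flare: "anterior chamber flare 3+ (marked, iris and lens details hazy), or"
- vitreous haze: "vitreous haze 3+ (Ophthalmology 1985; 92:467-71"

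A non-response condition applies to all three: "that fails to improve by 2 steps (or to grade 0) during a 6-week period".

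The event is one of five components of the primary outcome and of the DLE. Each component must also fall within six weeks of administration and be judged at least possibly due to the product and not to the operation alone.

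SAP 2.1 repeats the component as "Severe unresponsive inflammation (defined in Section 4.2 of the protocol" and adds no grade of its own. It then states "This is the same criteria as the dose limiting event in the dose escalation phase" and "The adverse events preferred terms are identified in Attachment 2". Attachment 2 lists preferred terms for ocular inflammation, among them anterior chamber cell, hypopyon and uveitis, with no grade attached.

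**The concern.** A severity threshold for a safety event would normally be open at the top. Here the cell criterion has a lower and an upper limit, and neither document says how a count above 50 is classified. A programmer or adjudicator who applies the stated grade and range would count an eye at 26 to 50 cells and would not count, on that criterion, an eye with more.

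The component feeds two things: the reported primary safety proportion, and the DLE count that Protocol 4.3.2.2 uses to decide whether dosing continues and where escalation ends. Cohorts are small (three, expandable to six), so one unclassified eye can change a cohort's result.

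**Working it through.** The documents give no figure to reproduce, and the trial has no formal sample size calculation. The check is one of logic.

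**1. The definition as a rule.** Let C, F and H be the cell, flare and haze criteria, N the six-week non-response, and R the relatedness condition. The inflammation component is (C or F or H) and N and R.

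- Literal reading of C: 26 ≤ count ≤ 50.
- Minimum reading of C: count ≥ 26.
- The two differ only for counts of 51 or more.

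**2. Does the text already mean a minimum?** Three internal signs say that this cannot be taken for granted.

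- The main DLE list writes open-ended limits elsewhere: the acuity item is set at 15 letters or more, and the SUSAR item reads "Grade III or above non-ocular SUSAR (see section 5.11.3".
- Protocol 5.4.2.3(i), on expected post-operative inflammation, uses 2+ cells as the name of a single, moderate grade. There the plus sign belongs to the grade label and does not mean *or more*.
- The parenthesis states an upper limit of 50, which a pure minimum would not need.

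**3. Which eyes are affected?** In each row, N and R are assumed to hold.

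| Eye | Literal | Minimum |
|---|---|---|
| 26–50 cells | counted | counted |
| Graded 3+ at one visit, then 51 or more cells | counted | counted |
| 51 or more cells, with flare or haze 3+ | counted | counted |
| 51 or more cells, never 3+ on any marker, but acuity or endophthalmitis component met | counted through that component | counted |
| 51 or more cells, never 3+ on any marker, no other component met | **not counted** | counted |

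The second row is counted because the eye has met the cell criterion at a visit and has then worsened. Table 2 schedules ocular examination at days 1 and 3 and weeks 1, 2, 4 and 6, so there are several opportunities to record 3+. Only the last row is a gap. If N or R fails, the eye is not an event under either reading.

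**4. Effect where the gap applies (assumed cases).**

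- Cohort of 3 with one such eye and no other event: 1/3 under the minimum reading, 0/3 under the literal one.
- Cohort of 6 with two events, one of them such an eye: 2/6 = 33% against 1/6 = 17%. Protocol 4.3.2.2.5 ends escalation at two or more DLEs among 3 to 6 participants, so the first result meets that rule and the second does not.

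**5. Does the SAP close the gap?** No. Attachment 2 sets no upper grade, but it sets no lower grade either. To move from an ungraded preferred term to a severe event, the analyst must go back to the protocol's grade, which is the text in question.

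**The case against.** The strongest reply is that 3+ under the word *severe*, with a cited grading system, is naturally read as a minimum, and that the cell range merely explains the grade. The open-ended wording for acuity and SUSAR grade sits in the main list, whereas the grades sit in a separate note, so the contrast does not prove that a ceiling was intended. This stands to the extent that the text is ambiguous and does not state an exclusion. It does not remove the need to say which reading applies.

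A reader might infer that every eye above 50 cells is lost from the primary outcome. The documents do not support that: flare, haze, an earlier or later visit graded 3+, acuity loss or infective endophthalmitis can each bring the eye in.

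A reader might also infer that escalation would be blind to such an eye. That too goes too far. The safety committee reviews data before each escalation and may act on medically important events, and the cohort 2 and 3 rules extend to other clinically relevant events. The SAP separately tabulates and lists ocular-inflammation events of interest. However, the first-participant check in cohort 1 refers to DLEs alone, and committee discretion does not correct the reported primary proportion.

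Finally, it is tempting to say that flare and haze have the same hole. Neither is worded as a minimum, but the documents do not show that a grade above 3+ exists for them. Only the 50-cell limit can be verified from the text.

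**Conclusion.** The point holds in a limited form. As written in Protocol 4.2.1 and 4.3.2.1, and as taken over by SAP 2.1, the cell criterion is not met by an eye with more than 50 cells. That eye is missing from the primary outcome and the DLE count only if it is never graded 3+ on any marker and meets no other component. The examples of 1/3 becoming 0/3 and 2/6 becoming 1/6 also require non-response over six weeks and at least possible relatedness. How often this combination would arise cannot be derived from the documents.

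The point still merits correction because any error runs one way: the literal rule can leave out a more severe eye while counting a less severe one, in a component of the primary safety outcome.

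**What to change.** The sponsor should confirm whether 3+ is intended as a minimum for cells, flare and haze. If it is:

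- In Protocol 4.2.1 and 4.3.2.1, write *3+ or above* for each marker. For cells this means 26 or more, the protocol's existing lower bound, so no new threshold is introduced.
- In SAP 2.1, state the same minimum grade. In Attachment 2, say that the ocular inflammation terms count toward the primary outcome only when that grade and the non-response condition are met.

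If a single grade is intended, the documents should say so and state how a count above 50 is classified. In either case the four places should agree. The cost is a few words in the protocol and the SAP, with no added data collection or visits.
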